**Document History – Changes compared to previous final version of SAP**

Date	Time point	Reason for update	Outcome for update	Section and title impacted (Current)
30-Nov-2021	Prior to FPFV	Creation of first version	First version	NA
20-Oct-2023	Prior to LPLV	Protocol amended	Analysis will be done descriptively. No inferential statistical testing or statistical modelling will be implemented.	All sections
26-Oct-2023	Prior to LPLV	Protocol amended	PK analysis is added.	

## List of abbreviations

AE	Adverse Event
BE	Blinded extension
BL	Baseline
CRF	Case Report Form
CSF	Cerebrospinal fluid
CSR	Clinical Study Report
DMS	Document Management System
DR	Dose response
DRF	Dose range finding
EoS	End of Study
FAS	Full Analysis Set
HD	Huntington's disease
HTT	Huntingtin
IA	Interim Analyses
MedDRA	Medical Dictionary for Drug Regulatory Affairs
mHTT	Mutan huntingtin
MI	Multiple imputation
OLE	Open-label extension
PBO	Placebo
PK	Pharmacokinetics
PPS	Per-Protocol Set
PRO	Patient-reported Outcomes
RAP	Reporting & Analysis Process
SAP	Statistical Analysis Plan
SAS	Statistical Analysis System
SD	Standard deviation
TFLs	Tables, Figures, Listings
UHDRS	Unified Huntington's Disease Rating Scales
Vol	Volumetric
WHO	World Health Organization

## 1 Introduction

[figure not shown]
This document contains details of the statistical methods and the analysis strategy that will be used in the phase 2b study CLMI070C12203 based on protocol version 02 (30th -Jan 2023). As per the USM (6th-Dec-2022) and protocol version 02, study drug was permanently discontinued in all participants and no further cohorts will be initiated. Hence, only an abbreviated clinical study report (CSR) will be created for this study.

### 1.1 Study design

The original study design was a staggered cohort approach with three potential active treatment arms. However, due to safety concerns, an USM (6th-Dec-2022) was issued to early terminate the study drug. Therefore, only cohort 1 data is available for analysis:

Treatment Arm A: Branaplam 56 mg oral solution or matching PBO, once weekly

**Figure 1-1 Study Design Overview**

#### 1.1.1 Primary estimand(s)

Not applicable due to early termination.

### 1.2 Study objectives and endpoints

As per the USM follow-up notification dated 06-Dec-2022, the original objectives are no longer applicable due to permanent discontinuation of study treatment. No statistical modelling will be done. **Table 1-1** indicates the original planned objectives, endpoints and which of those will be summarized descriptively for the CSR.

**Table 1-1 Original objectives and related endpoints**

Original objective(s)	Original endpoint(s)	Will be reported in CSR
Primary objective(s)	Endpoint(s) for primary objective(s)	

 
To assess the dose-response relationship of branaplam administered over 16 weeks on mHTT protein change from baseline in CSF
 
	
 
Period: From baseline to Week 17 over the Dose Range Finding (DRF) 
 
Reduction (%) of mHTT protein in CSF from baseline to Week 17. See Section 2.1 for Primary Estimand
 
 
 
	
 
mHTT protein in CSF
 

 
To evaluate the safety and tolerability of branaplam when administered for 16 weeks or longer in participants with HD.
 
	
 
Safety and tolerability parameters/assessments including but not limited to adverse events, physical exam (including neurological examination), findings, clinical laboratory assessments, HTT lowering, etc.
 
	
 
AEs
 
Neurological exams and nerve conduction studies
 
Labs, vital signs, ECG and etc (details in Section 2.7)
 

Secondary objective(s)	Endpoint(s) for secondary objective(s)	

 
To assess the pharmacodynamics of branaplam in participants with HD on clinical, imaging, and biomarker endpoints relevant to HD.
 
	
 
The following endpoints will be assessed over three periods: 
 
DRF: change from baseline to Week 17 compared to placebo
 
Core: change from baseline to the end of Core compared to placebo
 
Core + OLE: change from baseline and baseline-extension to week 53-extension
 
 
 
Ventricular, Caudate and Total Brain Volume as measured by structural magnetic resonance imaging (MRI)
 
Unified Huntington's Disease Rating Scale (UHDRS) Total Functional Capacity (TFC), UHDRS Total Motor Score (TMS), UHDRS Independence Scale (IS).
 
 
 
	
 
VolMRI ventricular, caudate and total brain volume
 
UHDRS TFC, TMS and IS
 

Original objective(s)	Original endpoint(s)	Will be reported in CSR
	

Concentrations of total HTT and mHTT protein in CSF and plasma

	

To assess pharmacokinetics of branaplam and its metabolite UFB112 in plasma and CSF

	

PK parameters (e.g. area under the curve (AUC)last, AUCtau, maximum concentration (Cmax), Tmax) of branaplam and its metabolite UFB112 in plasma after first dosing and at the end of the DRF Ctrough of branaplam and UFB112 in plasma across the study duration

Concentrations of branaplam and its metabolite UFB112 in CSF and concentration ratio CSF/plasma of the analytes

	

PK concentration and parameters (details in Section 2.6)

Exploratory objective(s)	Endpoint(s) for exploratory objective(s)	

Original objective(s)	Original endpoint(s)	Will be reported in CSR
	[REDACTED]	

• To explore the effects of branaplam in patients with HD on pharmacodynamic biomarkers relevant to HD

	

• The following endpoints will be assessed over three periods:

1. DRF: change from baseline to Week 17 compared to placebo

2. Core: change from baseline to the end of Core compared to placebo

3. Core + OLE: change from baseline and baseline-extension to week 53-extension

• NFL in serum and CSF

	

• NFL in serum and CSF

	[REDACTED]	

Original objective(s)	Original endpoint(s)	Will be reported in CSR
[REDACTED]	[REDACTED]	
[REDACTED]	[REDACTED]	

## 2 Statistical methods

### 2.1 Data analysis general information

Due to early termination, the original planned analysis of primary, secondary and exploratory endpoints to demonstrate efficacy and dose range finding are no longer applicable. There was only one cohort (with one active dose of branaplam) initiated in the core study period and the open label extension (OLE) period is no longer applicable. Therefore, all analysis will be performed over one period and no analysis will be performed based on OLE.

Statistical analysis will be performed using SAS® statistical software (SAS Institute, Cary, NC, USA.) version 9.4 or higher.

Unless specified differently, descriptive summary statistics for continuous variables include mean, median, standard deviation, Q1 (25th percentile), Q3 (75th percentile), minimum and maximum, and geometric mean (where appropriate), while for categorical variables frequencies and relative percentages will be reported.

#### 2.1.1 General definitions

##### Treatment groups

Due to USM, only Cohort 1 was initiated. All analysis will be performed by treatment group within cohort 1:

- Cohort 1: LMI070 56 mg and Placebo

##### Study Day

Day 1 is defined as the date when the study treatment is started. Study day is defined as the number of days since the date of study treatment (Day 1). Therefore, for a particular date, study day will be calculated as follows:

- for dates on or after Day 1:

Study day = Assessment date – Day 1 + 1;

- for dates prior to Day 1:

Study day = Assessment date – Day 1.

## Baseline

The baseline value is defined as the last assessment performed prior to start of study treatment. In this study, baseline values will be the values obtained during screening, the week of Baseline or on Day 1. If the Baseline visit is missing or the assessment was not done at Baseline, the last assessment of an earlier visit (scheduled or unscheduled) which is the closest to the Baseline visit will be used as Baseline. In case an assessment is repeated at a later visit during the screening/baseline epoch, the latest one will be used as Baseline. Note: Assessments on the day of randomization are assumed to have been taken as per protocol, i.e. if the assessment should be performed before dosing, the assessment will be treated as pre-dose as per protocol. Practically, i.e. that the time part of the date/time entry will be ignored. Exception: In case there is a protocol deviation or a comment that specifically indicates that the assessment has been taken post-dose, the assessment will not be treated as pre-dose.

## Post-baseline measurement

Post-baseline measurements are defined as those assessments after the first dose of treatment.

When change from baseline is of interest the following formula will be used for each scheduled visit and time-point where baseline and post-baseline values are both available **except** for volumetric (vol) MRI:

Change from baseline = post-baseline value – baseline value.

Percent (%) change from baseline = (post-baseline value – baseline value)/baseline value\*100%.

Annualized change from baseline = 365.25\*change from baseline/ time interval (in days).

Annualized percent change from baseline = 365.25\*percent change from baseline/time interval (in days).

Time interval = (date of current assessment – date of baseline assessment + 1).

Note for MRI data, change is derived via BSI technique, the changes are already provided in source data (calculation of change and % change for MRI is available in [Section 2.6.2.2](#)).

## Prior and Concomitant Medication

Prior medication will be defined as any non-study medication taken prior to the first dose of the study drug, irrespective of whether the medication continued into the treatment period.

Any non-study medication administered at least once between the day of first dose of study drug and end of the study will be a concomitant medication.

Therefore, some medications can be categorized as both, prior and concomitant medication.

## Age at clinical HD diagnosis

It should be estimated from date of clinical HD diagnosis and age at screening as follows:

Age at screening+ rounded (down) difference in years between date of clinical HD diagnosis and screening date. If partial date is available for HD diagnosis, impute as follows:

- If only day is missing (year and month are available): impute as the first day of the month (01/MON/YYYY)
- If both day and month are missing (only year is available): impute as mid date of the year (01/JUL/YYYY)

In case HD diagnosis occurred in the same year as screening, the difference will be set to 0 (instead of rounding down).

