5.1 Inclusion criteria

Participants eligible for inclusion in this study must meet **all** of the following criteria:

1. Signed informed consent must be obtained prior to participation in the study.
2. Must be capable of providing informed consent (in the opinion of the Investigator)
3. Clinically diagnosed Stage 1 or 2 Huntington's disease with a diagnostic confidence level (DCL) = 4 and a UHDRS Total Functional Capacity (TFC) >8 at screening
4. Genetically confirmed Huntington's disease, with presence of ≥ 40 CAG repeats in the huntingtin gene.
 - For participants without prior documentation, a sample must be sent to the central study laboratory and confirmation of the CAG repeat length for these participants must be obtained prior to randomization
 - For participants with previously existing documentation of their CAG repeat length, it is acceptable to use this prior data to qualify for randomization. These participants must also submit a sample for CAG repeat testing to be conducted by the central study laboratory.
5. Male and female participants between 25 to 75 years of age, inclusive, on the day of Informed Consent signature

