6.1 Study treatment

As per the USM follow-up notification dated 06-Dec-2022, the study treatment has been permanently discontinued; the last dose administered was 08-Aug-2022.

The investigational treatment for this study is branaplam and matching placebo. Novartis will supply branaplam and matching placebo in 6 mL vials containing 5 mL of study treatment. The vials will be packed in boxes containing 4 vials each. All eligible participants will be randomized via Interactive Response Technology (IRT) to one of the available treatment arms.

Details on the requirements for storage and management of study treatment, and instructions to be followed for preparation /dispensing, and administration of study treatment are outlined in the Instructions for Use.

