### **2.3.2 Demographics and other baseline characteristics**

#### **Summary tables**

Patient demographics will be summarized with descriptive statistics for the SAF by treatment and overall. Parameters include:

- Age (at screening)

- Sex
- Race
- Ethnicity
- Height
- Weight
- BMI
- Educational level, years of education
- Smoking and alcohol history
- Country/region

Summary of HD history will include:

- CAG repeat length (larger allele from central lab)
- CAG age product (CAP) score defined as
  - Definition 1: CAP score = (length of CAG repeat – 35.0) × age at screening
  - Definition 2: CAP score = (length of CAG repeat – 30.0)/6.49 × age at screening
- Family history:
  - a Parent affected: (only) mother affected, (only) father affected, both parents affected, no parent affected, and unknown
- Age at clinical HD diagnosis (defined in [Section 2.1.1](#))

Other baseline characteristics:

- Unified Huntington's Disease Rating Scales (UHDRS)
  - Total Function Capacity (TFC)
  - Total motor score (TMS)
  - Independence scale (IS)

- mHTT protein in CSF
- volMRI by region

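### The SAP rule for age at clinical HD diagnosis rounds a negative difference away from zero, which biases one descriptive baseline item downward by roughly 0.2 to 0.5 year under plausible assumptions

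*SAP*

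**What the plan says.** SAP 2.1.1 introduces the variable as an estimate: "It should be estimated from date of clinical HD diagnosis and age at screening as follows". The formula is "Age at screening+ rounded (down) difference in years between date of clinical HD diagnosis and screening date".

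Two rules for partial diagnosis dates follow: "If only day is missing (year and month are available): impute as the first day of the month (01/MON/YYYY") and "If both day and month are missing (only year is available): impute as mid date of the year (01/JUL/YYYY"). The definition closes with an exception: "In case HD diagnosis occurred in the same year as screening, the difference will be set to 0 (instead of rounding down").

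SAP 2.3.2 lists the result among the HD history items to be summarised: "Age at clinical HD diagnosis (defined in" Section 2.1.1). Neither document states whether age at screening is in whole years or decimals, or gives any distribution of time since diagnosis.

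**The concern.** The plus sign works only if the difference is diagnosis date minus screening date, which is negative. A positive difference would place diagnosis after screening. Rounding a negative number down increases the amount subtracted. The exception supports this reading: it replaces rounding down by 0 for a same-year diagnosis, whereas rounding toward zero would already give 0 for any gap of less than a year.

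If age at screening is itself in completed years, it has already been rounded down once, and the rule rounds down again in the same direction. The exception seems to depend on the calendar year and not on elapsed time, so the turn of the year alone can change the result by one.

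What is at stake is the accuracy of one reported disease characteristic in the baseline table.

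**Working it through.** **Inputs.** The formula, exception and imputation rules come from SAP 2.1.1. Ages 25 to 75 come from Protocol 5.1. The screening window is inferred as December 2021 to July 2022: the SAP document history dates its first version, 30-Nov-2021, before first patient first visit, and Protocol 6.1 says "the last dose administered was 08-Aug-2022". The plan states no error figure, so there is none to reproduce.

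**Assumptions not in the documents.** Age at screening is in completed years and birthdays are uniform. Time since diagnosis is uniform on 0-2, 0-5 or 0-10 years, or exponential with mean 1, 2, 3 or 5 years. Between 0% and 100% of dates are partial.

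**Algebra.** Let exact age at screening be a + f and time since diagnosis k + g, with a and k whole years and f and g fractions.
- True completed age at diagnosis: a - k if f ≥ g, otherwise a - k - 1.
- SAP rule outside the exception, with g > 0: a + floor(-(k + g)) = a - k - 1. This is one year too young whenever f ≥ g, and never too old with full dates. For independent uniform f and g, the probability is 0.5.
- SAP rule inside the exception: a. This is one year too old if a birthday fell between diagnosis and screening.
- Nearest-year rounding: too old if g < 0.5 and f < g (∫ g dg from 0 to 0.5 = 0.125); too young if g ≥ 0.5 and f ≥ g (∫ (1 - g) dg from 0.5 to 1 = 0.125). In total 25% are wrong and the mean error is zero.

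**Worked records.**
- Exact age 50.8 (recorded 50), diagnosed 2.3 years earlier: exact age at diagnosis 48.5, so 48 in completed years. The SAP rule gives 50 + (-3) = 47. Nearest-year gives 50 - 2 = 48.
- Screened 20 January 2022 at recorded age 50, with no birthday in the interval. Diagnosis on 20 December 2021 (31 days before) gives 50 - 1 = 49. Diagnosis on 5 January 2022 (15 days before) gives 50. The true age is 50 in both cases.

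**Simulation with calendar dates, 1,000,000 records per scenario, SAP rule.**

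| Scenario | Wrong | Too young | Too old |
|---|---|---|---|
| Dec 2021-Jul 2022, full dates, seven durations | 41.9-48.5% | 36.1-47.2% | 1.1-6.9% |
| Same window, exponential mean 3 | 47.4% | 44.3% | 3.1% |
| Full-calendar-year window, full dates, seven durations | 41.5-48.4% | 31.7-46.7% | 1.7-10.4% |
| Exponential mean 3, with partial dates | 41.8-50.8% | most of the errors | minority |

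The mean error is the too-old share minus the too-young share. For exponential mean 3 it is 0.031 - 0.443 = -0.41 year. The ranges in the first row bound it between 0.011 - 0.472 = -0.46 and 0.069 - 0.361 = -0.29. With the full-calendar-year window it runs from -0.21 to -0.45. Within the screening year, about 24-33% are wrong with full dates, all too old.

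**Alternatives.**
- Exception removed alone, exponential mean 3: 52.6% wrong against 47.4%. With the full-calendar-year window, the mean error goes from -0.38 to -0.53.
- Truncation toward zero, full dates: 42-50% wrong, all too old.
- Nearest year, full dates: about 25% wrong, mean error -0.00 to +0.04. If every date is year-only (exponential mean 3, full-calendar-year window), 33.3% are wrong against 49.8% under the SAP rule, with mean error about 0.

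**The case against.** The strongest reply is that the SAP calls this an estimate and builds it without birth date. Protocol 8.2 lists participant age, not birth date, and makes demographic collection subject to country rules. Some one-year errors are unavoidable, and nearest-year rounding still leaves about a quarter. That is true of the error rate but does not excuse the direction: the bias comes from the rounding rule and can be removed with the same data.

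The exception also has a plausible purpose. For a year-only date, the calendar year is all that is known, and an imputed 1 July can fall after screening only when diagnosis and screening share a year. That stands, and any replacement must cover the case.

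Three stronger readings are tempting but not supported:
- **That nearly half of ages are wrong, as a fact.** The rate depends on assumptions the documents do not supply. It also comes mainly from combining completed-year age with whole-year rounding, since truncation is wrong about as often. Rounding down sets the direction.
- **That the calendar-year exception causes the problem.** It lowers the overall error rate and the bias.
- **That participants with short disease histories are misordered in the analysis.** SAP 2.3.2 lists no disease duration, and no listed analysis ranks participants by this variable.

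**Conclusion.** Followed as written, the rule biases age at clinical HD diagnosis downward. The direction follows from the text, with the exception read as calendar year. The size is conditional: about 42-51% of participants off by one year, mostly too young, and a mean bias of about -0.2 to -0.5 year, under completed-year screening age, uniform birthdays and the durations tried.

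If age at screening is decimal, the result outside the screening year is too young by 1 - g, about half a year on average. If the exception instead means within 12 months, about 48-51% are still wrong, but with very recent diagnoses the errors are no longer mostly too young: for exponential mean 1 and a full-calendar-year window, 21.4% are too young, 26.5% too old, and the mean error is +0.05.

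The importance is low. This is one descriptive line, derived identically in both groups, in an abbreviated report without inferential testing. CAP score in SAP 2.3.2 uses age at screening and is unaffected, as are the mHTT and safety analyses.

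**What to change.** In SAP 2.1.1, define age at diagnosis as age at screening minus (screening date minus diagnosis date)/365.25, with the subtracted amount rounded to the nearest whole year and not allowed below 0 when an imputed date falls after screening. State whether age at screening is in completed years.

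Drop the same-year exception in the same change. Removing it alone would increase the bias, and the lower limit of 0 takes over its protection against imputed dates after screening.

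If birth date is held, derive completed years from birth date to diagnosis date directly; this is exact when both dates are full. The cost is one SAP sentence and one derivation line, with no new data.

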### On/off treatment

On treatment flag will be created for efficacy and safety endpoints including sNFL, volMRI, clinical endpoints, Nerve Conduction Studies (NCS), neuro exam, neuropathy symptoms [REDACTED] at visit level. An assessment is defined as on treatment if the collection date  $\leq \{ \text{last dosing date} + 13 \}$ . An assessment is defined as off treatment if the collection date  $\geq \{ \text{last dosing date} + 14 \}$ .

### Visit windows

Visit-windows will be used for by visit summary tables. For any assessment, there are the protocol defined scheduled visits around which visit windows were created to cover the complete range of days within the study. When visit windows are used, all visits will be re-aligned, i.e., they will be mapped into one of the visit windows.

However, for figures that involves individual trajectory (NFL, volMRI, mHTT) and for reports related (regarding worsening and recovery) to Neuro exam or Neuropathy questionnaire, an additional analysis visit based on actual analysis time (in weeks) instead of mapped windows will be used. This will be derived as ceiling of  $\{ \text{ADY}/7 \}$ . ADY is study day defined in [Section 2.1.1](#).

Details on calculation of visit windows based on the protocol will be provided in [Section 5.4](#).

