- Increased serum neurofilament light chain (sNfL) levels observed in more than half of the participants after 9 weeks on treatment
- Decreased amplitude in the sural nerve (SNAP) compared to baseline in the 3 participants with both an increase in sNfL and decreased or absent DTRs
- Paresthesia in the lower extremities was reported by two participants. One resolved on treatment within 5 days and one led to early treatment discontinuation and subsequently resolved.

In this communication:

Participants that were actively taking study treatment at the time were instructed to stop the study treatment immediately and to return to the site for an on-site visit no later than 7 business days after being informed of the USM. The USM letter provided details on the assessments to be conducted during that visit. Subsequent to this on-site visit participants were to continue to adhere to their monthly visit evaluation schedule for on-site visits as per protocol (e.g., Week 9, 13, 17, 21, 25 etc.) until further notice. During these visits, all scheduled assessments were to be performed as per protocol with the following exceptions:

- Study drug should no longer be taken by participants
- PK [REDACTED] including mHTT/HTT (plasma [REDACTED]) [REDACTED] should only be collected up to 6 weeks after the last dose of study drug. The 0-Hour timepoint (pre-dose in the protocol pre-USM) is the only required timepoint for collection.
- No additional lumbar puncture will be scheduled thereafter unless deemed necessary by the investigator.
- Follow-up Nerve Conduction Study (NCS) evaluation may be required on a case-by-case basis, in consultation with the DMC.

Participants that had already permanently discontinued study treatment and had scheduled an End of Treatment (EOT) and/or follow up assessments at the time of this USM were to continue the previously agreed upon schedule of assessments as per discussions between investigator and Sponsor.

Subsequently a **Follow-up IN (24-Oct-2022)** was sent to sites to provide an update on activities related to the ongoing study following the initial communication on 05-Aug-2022. No new changes were implemented as the purpose was to remind of the above schedule of assessments exceptions.

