Following a 6-week Screening period, patients will complete a baseline assessment (can be performed over a 6 day time frame) and a multi-dose, treatment period (with duration varying across patients) at the assigned treatment arm. Safety, tolerability, PD biomarker (fluid and images), PK and clinical endpoints relevant to HD will be collected as outlined in the assessment schedule.

The Screening period may be extended beyond 6 weeks in some cases. See [Section 8.1](#).

After confirming eligibility, participants will be randomized to an open cohort to receive either active or PBO treatment as an oral solution administered once weekly. Although a maximum of 3 treatment arms are planned, timing during the ongoing recruitment will determine which available treatment arms are actively recruiting (refer to [Figure 3-1](#)). In addition, not all treatment arms may be initiated, as it is dependent on the available safety profile, PK and mHTT lowering data. Participants will receive at least 16 weeks of treatment and will remain on the initially assigned treatment arm during the Core Period in the BE until IA is completed and optimal dose(s) selected for OLE. After dose selection, which may be more than one selected dose, patients will continue participation in OLE.

Post-USM: As per the USM follow-up notification dated 06-Dec-2022, the study treatment has been permanently discontinued and only Cohort 1 was enrolled. Participants who received active treatment (branaplam) will remain in the study for follow-up for approximately one year following initial treatment discontinuation.

Open-Label Extension (OLE)

OLE is no longer applicable due to permanent discontinuation of study treatment.

Once the optimal dose(s) is/are selected, sites will be notified and active participants will roll over to OLE at a subsequent study visit. The specific timing for each patient will be determined based onsite readiness to conduct the OLE. Prior to commencing dosing in OLE, a series of assessments (re-baselining) may be collected, as outlined in the assessment schedule [Table 8-2](#). If more than one dose is selected for the OLE, then patients will be re-assigned via IRT to one of the selected open label doses.

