#### Summary tables

- Summary statistics of raw, change, % change and annualized % change by visit and by on/off trt and by brain region

- Repeat after excluding Participants with subdural hematoma

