### **Summary tables**

- Summary statistics of raw values and change from BL by visit and by on/off trt (serum only)
- Frequency table for participants who had any increase together with the information about recovery (yes/no) at the end of observation.
- Repeat for subgroup of participants with at least 9 weeks of treatment

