## **5.4 Visit windows**

In general, if two consecutive visits  $V_t$  and  $V_s$  are  $x$  days apart, the upper limit of the visit window for  $V_t$  will be  $V_t+x/2$  and the lower limit for the visit  $V_s$  will be  $V_s-x/2 + 1$  (if  $x$  is even). The algorithm needs to ensure that visit windows are not overlapping and that there are no gaps, such that each assessment can be uniquely allocated to one visit window.

Both scheduled and unscheduled assessments will be considered.

In case of competing assessments within a visit window:

- For efficacy parameters: the assessment value closest to the scheduled visit day will be used. In case of equal distances, the earliest assessment value will be used.
- For safety parameters: the worst assessment value within the visit window will be used (see [Section 5.4](#)). If more than one assessments are equally worst, the one closer to visit window will be used.

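### Off-treatment MRI and serum NfL are tabulated by weeks since first dose, so the rows mix different times off drug and give no clean time course after stopping

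*SAP*

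**What the plan says.** After the Urgent Safety Measure (USM), Protocol Section 3 states that branaplam participants "will remain in the study for follow-up for approximately one year following initial treatment discontinuation". The Amendment 02 rationale gives the purpose as following peripheral neuropathy and collecting more MRI. It also describes the stop: "Participants that were actively taking study treatment at the time were instructed to stop the study treatment immediately". The last dose in the trial was on 08-Aug-2022, and some participants had already stopped permanently.

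The analysis clock starts at first dose. In SAP 2.1.1, "Study day is defined as the number of days since the date of study treatment (Day 1", and "Visit-windows will be used for by visit summary tables". Under On/off treatment, "An assessment is defined as off treatment if the collection date" is 14 or more days after the last dosing date. There are no categories of time off drug.

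The two tables concerned are:
- Volumetric MRI (SAP 2.6.2.2): "Summary statistics of raw, change, % change and annualized % change by visit and by on/off trt and by brain region".
- NfL (SAP 2.11.1): "Summary statistics of raw values and change from BL by visit and by on/off trt (serum only". CSF NfL has no on/off split.

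For MRI, SAP Table 5-6 sets the windows at study days 2–169 (Week 17), 170–295 (Week 33), 296–421 (Week 53) and 422 to end of study (Week 69).

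**The concern.** The follow-up year is meant to show what happens after the drug is stopped, so its natural clock is time since last dose. Dosing ended by calendar date in a cohort that entered over time, so weeks treated differ between participants. At a fixed study week, weeks off drug equal study week minus weeks treated. A lower value in an off-treatment row may then reflect longer recovery or less exposure, and the row cannot separate the two. The make-up of the rows also shifts, because the earliest off-treatment rows can hold only late entrants and early stoppers.

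The report is descriptive only, so the choice of time axis decides what a reader can see. At stake is whether the MRI and serum NfL tables show a course after stopping or a blend of courses.

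**Working it through.** **1. The plan's windows.** The SAP 5.4 midpoint rule, applied to target days 113, 225, 365 and 477, gives upper limits 113 + 56 = 169, 225 + 70 = 295 and 365 + 56 = 421. These match Table 5-6, so the MRI windows are confirmed as counted from Day 1. The window table for serum NfL is not visible in the public copy; for serum NfL the point rests on the general rule in SAP 2.1.1.

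**2. Time off drug.** A Week W visit falls on Day 7(W − 1) + 1, and the n-th weekly dose on Day 7(n − 1) + 1. With no missed doses, weeks off drug = W − n.

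**3. Spread of exposure.** No first-dose dates are given, so it has to be bounded.
- Long end: the Amendment 02 rationale reports findings after 13 weeks on treatment at the DMC review of 28-Jul-2022. If this means the Week 13 visit (Day 85) had been reached, first dose was by 05-May-2022, which makes 08-Aug-2022 Day 96 or later. If 13 full weeks had been completed, it is Day 103 or later.
- Short end: the SAP version of 26-Oct-2023 predates the last participant's last visit. If that is a Week 69 visit (Day 477, at most 14 days late, so Day 491), first dose was on or after 26-Oct-2023 minus 490 days = 23-Jun-2022. That makes 08-Aug-2022 Day 47 or earlier.
- Spread: 96 − 47 = 49 days, or 7 weeks, at least.

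Day 47 allows 7 weekly doses. Taking 13 doses at the long end is slightly cautious and gives a 6-week spread:

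| Target visit | Weeks off, 7 doses | Weeks off, 13 doses |
|---|---|---|
| Week 17 | 10 | 4 |
| Week 33 | 26 | 20 |
| Week 53 | 46 | 40 |
| Week 69 | 62 | 56 |

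**4. Effect of window width.** The ±2-week visit tolerance after the USM widens Week 33 to 18–28 weeks. Last doses here fall on Day 43 (7 doses) and Day 85 (13 doses). Across the full MRI windows, the off-treatment row can span 2 weeks (the flag's minimum) to (169 − 43)/7 = 18 weeks at Week 17, and (170 − 85)/7 ≈ 12 to (295 − 43)/7 = 36 weeks at Week 33.

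**5. Outer bound.** The first SAP version, 30-Nov-2021, predates the first visit. First dose from about 08-Dec-2021 would allow 1 to 35 doses. Week 33 would then run from 32 weeks off drug to still on treatment, Week 53 from 18 to 52 weeks off, and Week 69 from 34 to 68. This range is possible, not shown.

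**6. Where it matters.** Suppose, purely as illustration, that an excess over baseline halves every h weeks after the last dose, so the remaining share is 0.5^(weeks off/h). For 7 versus 13 doses:
- h = 8: 42% v 71% at Week 17, 11% v 18% at Week 33, 2% v 3% at Week 53.
- h = 26: 77% v 90%, 50% v 59%, 29% v 34%.

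The mixing is largest early and small by Week 53.

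**The case against.** The strongest reply is that the SAP already addresses recovery. It plans recovery flags and a yes/no NfL recovery table at end of observation, repeated in those with at least 9 weeks of treatment. It plans recovery tables for the neurological exam, the neuropathy questionnaire and nerve conduction, and a combined table in 2.7.4.7. Trajectory figures use actual weeks, serum NfL lines change colour at on/off, and follow-up is plotted per participant with on/off shading. This stands. A reader might infer that the plan cannot answer whether findings reversed; the documents do not support that. What is missing is the time course.

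Three other stronger readings also fail:
- That Week 33 pools people a few weeks off drug with others off for over half a year. Without first-dose dates this is possible but unproven.
- That everyone stopped at once. Some had stopped earlier, which can add to the mix.
- That the neurological recovery summaries share the defect. They are participant-level and built on weekly windows.

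It is also fair that last-dose bins do not remove confounding. Visits after the USM are fixed at study Weeks 33, 53 and 69, so treated duration still largely decides who falls in which bin. Time since baseline then varies within a bin, which matters for MRI change in a progressive disease.

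The reply does not cover MRI. It has no recovery table, its plots have no stated on/off coding, and actual weeks are still counted from Day 1. No MRI or NfL output is aligned to last dose, although the SAP computes days from last dose to lumbar puncture for mHTT at Weeks 9 and 17.

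**Conclusion.** The point holds as a limitation of the off-treatment volumetric MRI and serum NfL tables. They mix times off drug by at least about 6–7 weeks at each target visit, more once the visit windows are counted, with longer treatment tied to shorter time off. The consequence is material through Week 33 and minor at Weeks 53 and 69, unless the true exposure range is much wider than the minimum. MRI is the stronger case; for serum NfL the coloured individual plots and the recovery table show part of the picture. CSF NfL is outside the point: it has no on/off split, and no further lumbar punctures were scheduled after the stop unless the investigator saw a need.

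The size rests on three assumptions: the 13-week statement refers to participants still dosing in August 2022, the last visit was a Week 69 visit within its window, and doses were weekly without gaps. The direction does not depend on them; it follows from staggered entry and a calendar stop.

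**What to change.** Keep the study-week tables and add the following:
- Supplementary tables and mean plots of volumetric MRI and serum NfL by weeks since last dose, using the last dosing date already needed for the on/off flag. Bins should run to the end of follow-up, beyond 52 weeks, since Week 69 visits can fall at 56–62 weeks off drug even under the minimum spread.
- The distribution of time off drug (n, median, range) for each existing off-treatment row.
- On/off colouring in the MRI spaghetti plots.
- Treated duration alongside each last-dose bin, because it and time since baseline still differ across bins.

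Report change from the last on-treatment MRI only for participants who have such a scan, and only if the vendor can supply the pairwise boundary shift integral. A Week 17 scan on Day 113 counts as on treatment only if the last dose was on Day 113 − 13 = 100 or later, so many may have none.

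The cost is one derived variable and a few more descriptive outputs. No new visits are needed, and the neurological recovery summaries stay as they are.
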